3.1 Study Rationale

Progesterone - A promising candidate for systemically administered therapy: An agent which has no demonstrable negative effects on healthy cells but kills cancer cells efficiently and selectively would be a significant step forward for GBM treatment. One such agent may be the neurosteroid progesterone. It is a natural hormone made by both males and females which influences functions of both the central and peripheral nervous systems [Guennoun et al., 2019; Stein, 2017]. As a natural hormone, progesterone is readily available, easy to administer, safe, and very inexpensive. It crosses the BBB rapidly and one of its key effects is to reduce the cerebral edema and inflammation that often accompany severe brain injuries from trauma, surgical excision of brain tissue, chemotherapy, or radiation [Adamson et al. 2009]. Progesterone has been shown to have a very high safety profile and limited side effects in clinical treatment for brain injury [Wright et al. 2007].

Is Progesterone Neuroprotective or Cytotoxic?

The dose matters (hormesis): Hormesis is a dose response phenomenon characterized by low-dose stimulation and high-dose inhibition, resulting either a J-shaped or an inverted U-shaped dose response (Fig. 1). Progesterone shows a typical inverted U-shaped hormetic effect, as we reported in GBM [Atif et al. 2015a; 2015b]. Several other drugs have also been reported to exert a hormetic effect, including some

[figure not shown]

Fig. 1: Hormesis

chemotherapeutic [Reynolds 2010; Bao et al. 2015] and neuroprotective drugs for stroke and trauma

[Calabrese 2008; Howard et al. 2017]. Therefore, it is of critical importance to select the right dose of a therapeutic agent.

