The pharmacokinetics data of the proposed test drug, Prolutex, reveal very high levels of serum P4 (Cmax) in human following a single subcutaneous injection. A single subcutaneous dose of 25 mg produces a Cmax = 57.8 ± 13.6 ; 50 mg dose produces a Cmax = 103 ± 24.5 ; and 100 mg dose produces a Cmax = 235 ± 62.6 (Cometti, 2015) (see **Section 4.1**).

Now, if we compare the normal/physiological levels of P4 in human (~0.3 ng/ml) with the Cmax produced by a single 25 mg dose of Prolutex (~58 ng/ml), we observe a **~192 folds increase** in serum P4 levels. These high levels of P4 in human serum are also **~2.9 folds higher** compared to the mice serum levels. Taken together, we do not expect any proliferative effect of P4 at a dose of 25 mg in GBM patients given the very high serum P4 levels after P4 administration.

Summary: The above discussion provides significant pre-clinical evidence that natural progesterone has activity against GBM cells/tumors and that the anti-tumor levels used in pre-clinical models is achievable within patients. Based on the accumulating data, we feel that it is warranted to test progesterone for safety/tolerability and efficacy in patients with recurrent GBM.

[figure not shown]

Fig 2. Serum P4 levels in mice serum by RIA. Data are expressed as means \pm standard error of the mean (SEM) different groups (n = 12) from two independent experiments. Significant difference: * $p < 0.001$ compared with vehicle group; # $p < 0.001$ compared with P50 group, 50 mg P4 dose; and P100 group, P4 100 mg dose.

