5.2 Dosing and Administration

Formulation: An aqueous formulation of natural progesterone complexed with 2-hydroxypropyl- β -cyclodextrin (Subcutaneous progesterone; IBSA Institut Biochimique SA, Lugano, Switzerland) will be used. An IND for this formulation will be cleared by the FDA and cross-referenced to support the present study.

Route of administration: Each dose (25-75 mg) will be given daily by subcutaneous injection using a tuberculin syringe with sterile technique. The site of injection will rotate along different sites (standard locations including abdomen, thigh) based on patient preference with at least 1 day break between reinjection of a particular site. Each injection will consist of 25-50 mg of drug in 1-2 ml with multiple injections to be used if higher doses of drug are called for per study.

Timing of administration: Drug will be injected subcutaneously at about same time in the AM \pm 3 hours each day.

Pharmacokinetic assessment (only 1st 3 patients at each dose cohort): Will only be done on the first three patients at each dose level cohort. Assessment time points will be start on day 1 of treatment. Blood draws will be performed immediately prior to drug administration (by subcutaneous injection). Subsequent blood samples will be obtained at 30 minutes, 1 hour, 2 hours, 4 hours, 6 hours and 8 hours following progesterone injection. One additional time point will be performed on day 8 just prior to drug injection on those days.

Dose Finding Phase (Part 1):

Patients will be enrolled sequentially and will follow a 3+3 design. The dose levels that will be potentially used are on the following table:

Dose Level	Dose of aqueous natural progesterone for injection (mg)
Level -1	25
Level 0	50
Level 1	75

Dosing will start at Dose Level 0 and will escalate or de-escalate according to the following rules:

Dose Level -1

- 0 of 3 with DLT → **expand Level -1 to 20 patients**
- 1 of 3 with DLT → 3 more at Level -1
 - 1-2 of 6 with DLT → **expand Level -1 to 20 patients**
 - 3-4 of 6 with DLT → consider stopping study
- 2-3 of 3 with DLT → consider stopping study

Dose Level 0

- 0 of 3 with DLT → move to Level 1
- 1 of 3 with DLT → 3 more at Level 0
 - 1 of 6 with DLT → move to Level 1
 - 2 of 6 with DLT → **expand Level 0 to 20 patients**

3-4 of 6 with DLT → drop to Level -1
2-3 of 3 with DLT → drop to Level -1

Dose Level 1

0 of 3 with DLT → **expand Level 1 to 20 patients**
1 of 3 with DLT → 3 more at Level 1

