1-2 of 6 with DLT → **expand Level 1 to 20 patients**
3-4 of 6 with DLT → **expand Level 0 to 20 patients**
2-3 of 3 with DLT → **expand Level 0 to 20 patients**

During the dose finding phase of the study, a treatment will be considered safe/tolerable if no DLT defined as \geq grade 3 toxicity during the first 4 weeks drug therapy not clearly due to the underlying disease or extraneous causes with exceptions as noted in **Section 5.3**. After treatment initiation of up to 6 patients at a dose level and continuation for a minimum of 4 weeks with AE assessment, enrollment to the next (higher or lower) dose level as determined by the rules will only start after data is presented to the Winship Data Safety Monitoring Committee (DSMC) and final approval is obtained for starting the next dose level.

Dose escalations will be reviewed by the Winship Data Safety Monitoring Committee (DSMC) (per Winship SOP 7.9 Dose Escalation Determinations for Sponsor-Investigator or Investigator Initiated Studies). The PI or designee will provide an update on all relevant safety data of patients entered to a dose level to the DSMC when dose escalation is planned. Upon obtaining approval from the DSMC, dose escalation can proceed.

Dose Expansion Phase (Part 2):

The purpose of cohort expansion is to gather additional safety and tolerability information, and evaluate the efficacy of aqueous natural progesterone for injection at the dose determined by the Dose Finding Phase of the study.

The PI or designee must provide the DSMC a report outlining the overall enrollment and path to decision for the escalation dose(s) selected.

Continuous evaluation of toxicity events in the cohort expansion will be performed throughout enrollment in the expansion cohort. If, at any time, the aggregate rate of treatment-related toxicities meeting DLT criteria exceeds 33% across all subjects treated in the expansion cohort, the findings will be discussed and further enrollment may be interrupted. Depending on the nature and grade of the toxicity and after assessing the risk:benefit ratio, a new dose(s) for all cohorts may be initiated at a previously tested lower dose level, or at a dose level intermediate to previously tested lower dose levels.

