5.4 Dose Modification

Progesterone will be withheld for any instance of a CTCAE v5.0 grade 3 or greater toxicity (except for grade 3 neutropenia or grade 3 thrombocytopenia without clinically significant bleeding). Drug may be resumed, at the discretion of the treating physician, if the toxicity has reduced to the grade 0-1 level within 14 days. Treatment will be discontinued if toxicity persists beyond 14 days. For toxicity not clearly due to the underlying disease or extraneous causes, 50% dose reduction of original dose will be used when resuming treatment after sufficient recovery of toxicity as defined above. If toxicity is clearly due to the underlying disease or extraneous causes, no dose reduction is required after sufficient recovery of toxicity as defined above. Treatment will also discontinue if there is development of a DLT after one dose reduction.

Progesterone will be discontinued if patient develops any specific contraindication for use of progesterone (e.g. thromboembolic event). The treating physician can also stop progesterone if he/she feels that doing so would be in the best interest of the patient.

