4. Action taken with respect to study or investigational treatment (none, dose adjusted, temporarily interrupted, permanently discontinued, unknown, not applicable)
5. Whether medication or therapy was given (no concomitant medication/non-drug therapy, concomitant medication/non-drug therapy)
6. Whether it is serious, where a serious adverse event (SAE) is defined above (**Section 16**) and which seriousness criteria have been met (include for NCDS trials).
7. Outcome (not recovered/not resolved, recovered/resolved, recovering/resolving, recovered/resolved with sequelae, fatal, unknown)

If the event worsens the event should be reported a second time in the CRF noting the start date when the event worsens in toxicity. For grade 3 and 4 adverse events only, if improvement to a lower grade is determined a new entry for this event should be reported in the CRF noting the start date when the event improved from having been Grade 3 or Grade 4. For phase I studies any AE that constitutes a DLT should be reported like a grade 3 and 4 adverse event. All adverse events should be treated appropriately. If a concomitant medication or non-drug therapy is given, this action should be recorded on the Adverse Event CRF.

Once an adverse event is detected, it should be followed until its resolution or until it is judged to be permanent, and assessment should be made at each visit (or more frequently, if necessary) of any changes in severity, the suspected relationship to the study treatment, the interventions required to treat it, and the outcome. Progression of malignancy (including fatal outcomes), if documented by use of appropriate method (for example, as per protocol-specified criteria for GBMs), should not be reported as a serious adverse event.

Adverse events separate from the progression of malignancy (example, deep vein thrombosis at the time of progression or hemoptysis concurrent with finding of disease progression) will be reported as per usual guidelines used for such events with proper attribution regarding relatedness to the drug.

Laboratory abnormalities that constitute an Adverse event in their own right (are considered clinically significant, induce clinical signs or symptoms, require concomitant therapy or require changes in study treatment), should be recorded on the Adverse Events CRF.

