Laboratory abnormalities, that do not meet the definition of an adverse event, should not be reported as adverse events. A Grade 3 or 4 event (severe) as per CTCAE does not automatically indicate a SAE unless it meets the definition of serious as defined below and/or as per investigator's discretion. A dose hold or medication for the lab abnormality may be required by the protocol in which case the lab abnormality would still, by definition, be an adverse event and must be reported as such.

Serious Adverse Event Reporting

For the time period beginning at treatment allocation/randomization through **28** days following cessation of treatment, or **28** days following cessation of treatment if the subject initiates new anticancer therapy, whichever is earlier, any serious adverse event, or follow up to a serious adverse event, including death due to any cause whether or not related to the study drug, must be **submitted on an SAE form** and assessed by PI in order to determine reporting criteria to IRB, DSMC, FDA, supporter or IND Sponsor.

All SAEs will be followed until satisfactory resolution or until the site investigator deems the event to be chronic or the adherence to be stable. Other supporting documentation of the event may be requested by the IND sponsor and should be provided as soon as possible. The IND sponsor-investigator ([name]) will be responsible for notifying FDA of any unexpected fatal or life-threatening suspected adverse reaction as soon as possible but in no case later than 7 calendar days after the sponsor's initial receipt of the information.

All Serious Adverse Events which occur during all periods of a clinical trial, independently of causal relationship, **must be reported immediately (i.e. within 24 hours after first knowledge)** by fax or email to:

IBSA – Drug Safety Unit
[contact]
[contact]
Email: [contact]

Actions in case of SAE/SAR:

When the Investigator receives knowledge of an SAE he/she is expected to proceed as follows:

1. Take the appropriate diagnostic and therapeutic measures to minimize the risk for the subject
2. Collect evidence for the elucidation of the relationship between SAE and the IMP
3. Fill in, in a clear and legible way, the SAE form (Type of report: initial) with all the information requested and fax or email it to IBSA - Drug Safety Unit within 24 hours after first knowledge,

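### Section 16 gives conflicting SAE rules for death from progression, no safety or Part 1 dose rule uses tumor growth, and the halving rule can leave the stated dose range

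*Combined protocol and SAP*

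**What the plan says.** **Reporting of deaths.** Section 16, Adverse Event Reporting, states that "Progression of malignancy (including fatal outcomes), if documented by use of appropriate method" should not be reported as an SAE. The next subsection, Serious Adverse Event Reporting, requires an SAE form for any serious event up to 28 days after treatment stops, "including death due to any cause whether or not related to the study drug". The principal investigator then decides whether it goes to the IRB, DSMC or FDA. Section 16 also collects every death on a Death form, with no stated route from that form to the DSMC.

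**The biological premise.** Section 3.1 says: "Hormesis is a dose response phenomenon characterized by low-dose stimulation and high-dose inhibition". It adds that the investigators have reported this effect for progesterone in GBM. Later in the same section, on exposure grounds, it says "we do not expect any proliferative effect of P4 at a dose of 25 mg".

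**Dose decisions.** In Part 1 (Sections 1.2 and 5.2) the dose moves on counts of dose-limiting toxicities (DLTs). Section 5.3 leaves out grade 3 or higher events that are clearly due to disease or extraneous causes. For each planned escalation, "The PI or designee will provide an update on all relevant safety data of patients entered to a dose level to the DSMC". Tumor volumes and progression deaths are not named.

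**Dose range.** Section 5.2: "Each dose (25-75 mg) will be given daily by subcutaneous injection". Section 5.4, for toxicity not clearly due to disease or extraneous causes: "50% dose reduction of original dose will be used when resuming treatment".

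**The concern.** Safety and tolerability is a primary objective, and the protocol itself names growth stimulation as something this drug can do at low dose. If that happened in a patient, it would look like progression. That is the one kind of event for which the SAE text contradicts itself, and the one kind of data that no Part 1 rule asks for. Toxicity also moves the dose downward, toward the side on which the rationale places stimulation.

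Two things are at stake. The count of deaths in safety reports could depend on which clause a staff member followed. And the DSMC could approve a new dose level, or a report on expansion, without having been shown tumor data that the trial already holds.

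**Working it through.** **1. The SAE clauses side by side.** Take a patient who dies of documented progression within 28 days of the last dose.
- Adverse Event Reporting: not an SAE.
- Serious Adverse Event Reporting: SAE form required.
- Death form: completed, with no stated link to the DSMC.

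The first two cannot both be followed.

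**2. What the dose rule responds to.** With DLT probability d per patient, the rule escalates from Level 0 on 0 of 3, or on 1 of 3 followed by 0 of 3:

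P(escalate) = (1-d)^3 + 3d(1-d)^2 × (1-d)^3

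| d | P(escalate) |
|---|---|
| 0.10 | 0.906 |
| 0.20 | 0.709 |
| 0.33 | 0.434 |

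Only d enters. Tumor growth affects the decision only through a grade 3 or higher event that is not judged clearly due to disease. Three of three patients with marked growth on the 4-week MRI, and no such event, count as 0 of 3 with DLT. That moves Level 0 up, or expands Level 1 or Level -1 to 20.

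**3. The plan's exposure argument.** Inputs: Cmax 57.8 ng/mL at 25 mg (Sections 3.1 and 4.1), physiological level 0.3 ng/mL and mouse level 14.91 ng/mL (Section 3.1).
- 57.8 / 0.3 = 192.7 (plan: about 192).
- (57.8 - 14.91) / 14.91 = 2.88 (plan: about 2.9).

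Both figures reproduce. However, the human value is a peak (Tmax 0.92 h, Section 4.1), and the mouse value was taken 24 h after injection. The documents give no human 24 h level, so the following is an assumed single-dose range for 25 mg, using the Section 4.1 table:
- Low: effective half-life = ln 2 × 349 / 57.8 = 4.19 h. Level = 57.8 × 2^(-(24 - 0.92)/4.19) = 1.3 ng/mL.
- High: terminal half-life 13.1 h applied from the peak. Level = 57.8 × 2^(-(24 - 0.92)/13.1) = 17.0 ng/mL. This curve implies an AUC of 57.8 × 13.1 / ln 2 = 1092 against the stated 349, so 17 is too high.

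Most of the range lies below 14.91 and all of it above 0.3. The 2.9-fold margin is therefore not shown on a like-for-like basis.

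**4. The halving rule.** 0.5 × 75 = 37.5 mg and 0.5 × 50 = 25 mg stay within 25-75 mg. 0.5 × 25 = 12.5 mg does not, and it is also below the 25-50 mg per injection in Section 5.2.

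**5. Can the tumor endpoints stand in?** The futility rule stops enrollment at 1 or fewer of 10 with stable disease or better: P(stop) = (1-p)^10 + 10p(1-p)^9.

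| True rate p | P(stop) |
|---|---|
| 0% | 1.00 |
| 5% | 0.914 |
| 10% (the plan's rate for ineffective therapy) | 0.736 |
| 20% | 0.376 |

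A harmful expansion dose would usually be stopped, but so would an inactive one. At the end, P(0 of 20 | 10%) = 0.9^20 = 0.122, with Clopper-Pearson upper limit 1 - 0.025^(1/20) = 16.8%. Zero responses would need at least 29 patients for one-sided p ≤ 0.05 (0.9^29 = 0.047).

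**The case against.** The documents contain more protection than a quick reading suggests.

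- **A reader might infer that the rationale predicts harm at the planned dose levels.** It does not. Section 3.1 expects no proliferative effect at 25 mg, the lowest level. That argument has the sampling-time weakness shown above, but a weak reassurance is not a prediction of harm.
- **A reader might infer that progression events are shut out of the safety data.** Only events clearly due to disease leave the DLT count. Section 16 says that the study product is always suspect. Section 5.3 requires review of all grade 2 or higher events before a higher level opens. For deaths, the text is an unresolved contradiction, not a settled exclusion.
- **A reader might infer that the trial cannot see tumor growth, or never examines abandoned dose levels.** Week-8 response is a primary endpoint, futility is checked at 10 patients, the study team reviews efficacy monthly, and PFS and OS are analyzed for all patients as well as the expansion dose. The DSMC's general remit includes risk-benefit, and calling its package safety data does not forbid tumor data.
- **The 12.5 mg case is conditional.** It needs de-escalation to Level -1 and then a patient who resumes after toxicity. Assuming dose-proportional Cmax, which Section 4.1 roughly supports, the peak would be 57.8 / 2 = 28.9 ng/mL, or 96 times 0.3 and 1.9 times 14.91. The protocol's peak-based argument could be extended to it.
- **A listing has no comparator.** Section 15.1 expects enhancing recurrences to progress without effective therapy, so growth in 3 of 3 patients would not show stimulation. Percent change is undefined where surgery left no enhancing disease.

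All of this stands, and it limits the point. It does not remove the SAE contradiction, bring tumor data into Part 1 decisions, or put 12.5 mg inside the stated range. PFS and OS come late and pool the dose levels. What Section 16 describes as going from the monthly meeting to the DSMC is adverse events.

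**Conclusion.** The point holds as a should-fix matter of safety oversight and consistency. Three parts rest on the text alone: the two SAE clauses conflict, no safety or Part 1 dose rule uses tumor growth, and the halving rule can give 12.5 mg against a stated minimum of 25 mg. Given the stated hormesis premise, they deserve more attention than they otherwise would.

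The existing tumor measures do not fill the gap. They do not enter Part 1 decisions, and at this size they cannot distinguish harm from inactivity (0.736 chance of a futility stop at the 10% reference rate; 0.122 for 0 of 20). The binomial figures take that 10% from the plan and assume independent patients. The 1.3-17 ng/mL range is an assumption and serves only to show that the peak-to-24-hour comparison leaves the question open.

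The documents do not support saying that stimulation is expected at the planned levels, or that the trial is unable to observe tumor growth.

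**What to change.** 1. Reconcile the two subsections of Section 16 on deaths from progression. Whichever way the SAE question is settled, list all deaths within 28 days of the last dose, with attribution, in each DSMC submission.
2. Add to each DSMC dose-level and expansion report a per-patient listing by assigned and actual dose: volume change at the 4-week MRI where there is measurable disease, progression status, and clinical deterioration attributed to progression. State that it is descriptive and cannot by itself separate stimulation from inactivity. The 4-week MRI window is ±3 days in Section 1.3 and ±1 week in Section 5.6. These must be reconciled so that it is clear whether the scan will be available when the report is due.
3. Reconcile the 50% reduction in Section 5.4 with the dose range in Section 5.2 and the 25 mg argument in Section 3.1. No dose is proposed here.

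The cost is wording changes and one extra listing, with no new visits or tests. The downside is that disease-related events will appear in safety reviews and need cautious interpretation in groups of 3 to 6 patients.

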APPENDIX 1 PERFORMANCE STATUS CRITERIA

ECOG Performance Status Scale		Karnofsky Performance Scale	
Grade	Descriptions	Percent	Description
0	Normal activity. Fully active, able to carry on all pre-disease performance without restriction.	100	Normal, no complaints, no evidence of disease.
		90	Able to carry on normal activity; minor signs or symptoms of disease.
1	Symptoms, but ambulatory. Restricted in physically strenuous activity, but ambulatory and able to carry out work of a light or sedentary nature (e.g., light housework, office work).	80	Normal activity with effort; some signs or symptoms of disease.
		70	Cares for self, unable to carry on normal activity or to do active work.
2	In bed <50% of the time. Ambulatory and capable of all self-care, but unable to carry out any work activities. Up and about more than 50% of waking hours.	60	Requires occasional assistance, but is able to care for most of his/her needs.
		50	Requires considerable assistance and frequent medical care.
3	In bed >50% of the time. Capable of only limited self-care, confined to bed or chair more than 50% of waking hours.	40	Disabled, requires special care and assistance.
		30	Severely disabled, hospitalization indicated. Death not imminent.
4	100% bedridden. Completely disabled. Cannot carry on any self-care. Totally confined to bed or chair.	20	Very sick, hospitalization indicated. Death not imminent.
		10	Moribund, fatal processes progressing rapidly.
5	Dead.	0	Dead.

As published in Am. J. Clin. Oncol.: Oken, M.M., Creech, R.H., Tormey, D.C., Horton, J., Davis, T.E., McFadden, E.T., Carbone, P.P.: Toxicity And Response Criteria Of The Eastern Cooperative Oncology Group. Am J Clin Oncol 5:649-655, 1982. The Eastern Cooperative Oncology Group, Robert Comis M.D., Group Chair

